Official Title: Pioneering Video-Based Neurocritical Care Education in Palestine: A Randomized Controlled Trial on Nursing Students' Knowledge, Attitude, Practice, and Self-Confidence Toward External Ventricular Drainage

ClinicalTrials.gov Identifier: Pending NCT Registration

Document Type: Study Protocol (with Integrated Statistical Analysis Plan)

Principal Investigator: [name], Modern University College, West Bank, Palestine

Date: Oct 2025

Study Protocol

1. Background and Rationale

External Ventricular Drainage (EVD) is a lifesaving neurosurgical procedure that monitors intracranial pressure and drains cerebrospinal fluid in patients with acute brain injury, hydrocephalus, or subarachnoid hemorrhage. Despite its importance, undergraduate nursing education in Palestine rarely includes practical or evidence-based EVD training. This educational gap leads to low confidence and preparedness among nursing students entering neurocritical care environments. Video-based learning has emerged as an effective method to improve cognitive and psychomotor skills through visual engagement and standardized instruction.

This randomized controlled trial (RCT) aims to evaluate the effectiveness of a theory-informed, video-based educational intervention compared to traditional flashcard learning in improving nursing students' knowledge, attitude, practice, and self-confidence toward EVD care.

2. Study Objectives

1. To assess the impact of video-based education on EVD-related knowledge, attitude, practice, and confidence among nursing students.
2. To compare post-intervention improvements between the video-based and flashcard-based learning groups.
3. To explore the correlation between baseline characteristics and post-intervention outcomes.

3. Study Design

A single-blind, parallel-group randomized controlled trial with a 1:1 allocation ratio.

4. Setting and Participants

The study will be conducted at Modern University College, West Bank, Palestine, during the Spring 2025 semester. Participants are third- and fourth-year nursing students enrolled in the critical care course who have not yet completed the nervous system module.

Inclusion Criteria:

- Active enrollment in the critical care course.
- Willingness to provide informed consent.
- Availability for both pre- and post-test assessments.

Exclusion Criteria:

- Prior clinical experience or coursework related to neurocritical care.
- Participation in another educational study during the same period.

5. Sample Size

Based on a power analysis (effect size $d = 0.6$, $\alpha = 0.05$, power = 0.80), a minimum of 45 participants per group (total $N = 90$) is required to detect statistically significant differences in post-test scores.

6. Randomization and Blinding

Participants will be randomly assigned using a computer-generated block randomization list (block size = 4). Group allocation will be concealed in sealed opaque envelopes. The study is single-blind: participants will know their group assignment, but assessors analyzing the data will be blinded.

7. Intervention

- **Intervention Group:** A 57-minute theory-informed video module demonstrating EVD procedures, nursing care principles, and infection control practices.
- **Control Group:** A flashcard-based learning session of equivalent duration covering identical content without audiovisual elements.

8. Outcome Measures

1. **Knowledge:** 11-item multiple-choice questionnaire (score range 0–11).
2. **Attitude:** 6-item Likert scale (1–5 per item).
3. **Practice:** 23-item self-reported checklist (1–5 per item).
4. **Confidence:** 10-point visual analogue scale (0–10).

9. Data Collection Procedure

Pre-test assessments will be conducted immediately before the intervention. Post-tests will be administered one week after completion. Demographic and baseline characteristics (age, gender, academic level, GPA) will also be collected.

10. Statistical Analysis Plan

Data will be analyzed using SPSS version 27.

- **Descriptive statistics:** Mean, standard deviation, frequency, and percentage.
- **Inferential statistics:**
 - Paired t-tests to assess within-group pre- and post-test changes.
 - Independent t-tests to compare between-group differences.
 - ANCOVA to adjust post-test outcomes for baseline values.
 - Effect sizes (Cohen's d) and 95% confidence intervals will be calculated.
- Significance threshold set at $p < 0.05$.

11. Ethical Considerations

Ethical approval will be obtained from the Institutional Review Board (IRB) of Modern University College. Participation is voluntary, and informed consent will be obtained electronically. Data confidentiality will be maintained, and all identifiers will be removed prior to analysis.

12. Expected Outcomes

The video-based educational intervention is expected to produce significantly greater improvements in knowledge, practice, and confidence compared to the flashcard group, with comparable attitudinal changes. The findings will support the integration of multimedia tools into neurocritical care education in undergraduate nursing curricula.

13. Dissemination Plan

Findings will be disseminated through peer-reviewed publications, conference presentations, and integration into nursing education policy recommendations. Results and supporting documents will be publicly available on ClinicalTrials.gov following study completion.

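### Does an October 2025 date on a plan for a Spring 2025 trial call for a change to the analysis plan?

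*Combined protocol and SAP*

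**What the plan says.** The title block describes the document as a "Study Protocol (with Integrated Statistical Analysis Plan"), so its one date, October 2025, covers both parts. The same block reads "ClinicalTrials.gov Identifier: Pending NCT Registration".

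Section 4 says, in the future tense, that the study will take place at the college "during the Spring 2025 semester". Participants are students "enrolled in the critical care course who have not yet completed the nervous system module".

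Section 9 fixes the last measurement: "Post-tests will be administered one week after completion". Section 6 says that "assessors analyzing the data will be blinded", while participants know their group. Section 11 says "Ethical approval will be obtained from the Institutional Review Board (IRB) of Modern University College".

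The visible text gives no version history and no dates for enrolment, data lock, unblinding or SAP approval.

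**The concern.** A plan dated after the semester in which it says the trial will take place invites the question of whether the analysis was written with the data in hand. If it was, results from Section 10 could not fairly be called prespecified, and the outcome-by-outcome predictions in Section 12 (gains in knowledge, practice and confidence, with attitude similar between groups) would carry less weight as hypotheses. Pending registration and an ethics approval still described as future raise the same question about what came before enrolment.

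The worry is sharper because Section 10 leaves room for choice. Section 8 lists four outcomes without naming a primary one, and Section 10 offers both an independent t-test and ANCOVA for comparing the groups. That gives 4 × 2 = 8 between-group results from which a favourable one could be picked after the event.

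The intended cohort may also look uncertain, since students enrolled in Spring 2025 are not those enrolled in a later semester.

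**Working it through.** **1. Order of the dates, read literally.** The documents do not say when the semester ended. As an assumption, take an end between 30 April and 31 July 2025. Section 9 adds 7 days to reach the post-test.

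- Semester ending 31 July: latest post-test 7 August. To 1 October is 24 + 30 + 1 = 55 days.
- Semester ending 30 April: latest post-test 7 May. To 1 October is 24 + 30 + 31 + 31 + 30 + 1 = 147 days.

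Under this assumed calendar, the document date falls at least 55 days after the last post-test of a Spring 2025 trial. No upper limit can be given. The intervention is one 57-minute module or an equivalent flashcard session, which could have been held at any point in the semester, so semester end plus 7 days is only a latest date. The order is clear if both dates are taken at face value; the size of the gap tells us nothing further.

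**2. What could explain the conflict.** At least three readings fit the text:

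- an older protocol, with October 2025 put on the file when it was prepared for registration;
- a misprinted semester, with the trial still to come;
- a plan written up after the data were collected.

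The future tense does not separate them. It is used throughout the protocol sections, so the ethics sentence is a matter of style and not independent evidence on timing. Missing approval dates prove little, because signature pages were removed from the text under review and enrolment dates belong to a registry record that is not available here.

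**3. Does any figure or rule depend on the date?** The plan's one computed figure comes from Section 5: d = 0.6, α = 0.05, power 0.80.

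- Normal approximation, two-sided: n = 2(1.960 + 0.842)² / 0.6² = 2 × 7.851 / 0.36 = 43.6, so 44 per group.
- Exact two-sided t-test: 44.59, so 45 per group, as stated; power at 45 is 0.804.
- One-sided, the answer would be 35, so the stated figure is two-sided.

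No date enters this calculation. The same is true of the block size of 4, the four scores in Section 8, the paired and independent t-tests, the ANCOVA on baseline, and the 0.05 threshold. The same data analysed under Section 10 give the same results whichever date is right.

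**4. The cohort.** Eligibility is set by course enrolment, module status and prior neurocritical experience or coursework. Those criteria read the same in any semester. Section 5 gives the number required, 90, but the document does not say how many eligible students there were in any semester, so a different semester overturns no stated recruitment figure.

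**The case for a change.** The best argument for acting is that the dates decide what can still be done. If the data are in but the allocation code has not reached the analyst, a signed and dated SAP could still fix the main analysis blind, and that chance is lost at unblinding. Asking for dates costs almost nothing, and with eight possible between-group results the answer is of real interest to a reader.

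Part of this stands. From this document alone nobody can confirm that the SAP came first, and the analyst blinding in Section 6 is an undated safeguard that does not extend to participants. A reader is entitled to the actual dates.

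It does not lead to a change in the plan, for three reasons. First, the request is for facts about conduct, and what follows from them depends on events the documents do not record. For example, registration can be called retrospective only if the actual dates show that it followed first enrolment. Second, supplying the dates alters no method. Third, the choice between t-test and ANCOVA, and the lack of a named primary outcome, are separate questions about Sections 8 and 10. They would exist unchanged under a perfectly consistent calendar and should be judged on their own merits.

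**Conclusion.** The conflict between the document date and the semester is genuine and unexplained in the visible text. It is a documentation slip or a gap in version history, and nothing in the document shows it to be a fault of design or analysis. It supports neither the statement that the SAP preceded the data nor the statement that it followed them.

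Its effect on the sample size, the estimates, the power and the calculated error rates is nil. The only consequence is for how the results may be described: prespecification can be claimed for analyses found in a version dated before unblinded data were seen, and registration should be described according to its actual order relative to first enrolment. Those are ordinary reporting duties, which the investigator can meet from the study records.

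This conclusion assumes that the October 2025 date and the semester are transcribed correctly. It does not depend on the assumed semester end dates, which were used only to confirm the literal order.

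### With one fixed block size of 4 and open assignment, up to a third of allocations could be known in advance if entry is sequential and enrolling staff can follow the sequence; Section 6 should rule this out

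*Combined protocol and SAP*

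**What the plan says.** Section 3 describes a "parallel-group randomized controlled trial with a 1:1 allocation ratio". Section 6 specifies a "computer-generated block randomization list (block size = 4", a single value with no mention of varying it. On concealment it says: "Group allocation will be concealed in sealed opaque envelopes". On blinding it says: "participants will know their group assignment, but assessors analyzing the data will be blinded".

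Section 5 asks for "a minimum of 45 participants per group", 90 in all. Section 9 places the pre-test in time: "Pre-test assessments will be conducted immediately before the intervention". Section 10 plans independent t-tests between arms and an ANCOVA adjusting for baseline, without saying which is the main comparison.

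The document does not say who generates the list, who enrols students, or who holds and opens the envelopes. It does not say whether students enter singly or as a class, whether an envelope is opened before or after the pre-test, or whether enrolling staff know the block size or see earlier assignments.

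**The concern.** An opaque envelope hides the next card. It does not stop someone who knows the earlier cards in a block, and the block's length, from working out what is left. With two places per arm in every block of 4, the last place is always determined, and the third is too whenever the first two match.

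The design leaves room for this. All students are on one critical care course at one college, participants know their arm, and the blinding statement does not cover enrolling staff. Section 12 also states in advance that video should do better on knowledge, practice and confidence, and practice and confidence are self-reported. Someone able to anticipate the next arm could bring forward a keener or stronger student when video is due. The arms would then differ at entry for reasons unrelated to the teaching. The t-tests cannot remove that, and ANCOVA removes only what the pre-test measures.

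**Working it through.** **Inputs.** From the protocol: block size 4 (Section 6); 1:1 ratio (Section 3); N = 90, d = 0.6, alpha 0.05, power 0.80 (Section 5). Assumed, because the protocol gives no figure: a steering shift δ of 0.1 to 0.3 SD per student, and a pre-post correlation ρ of 0.6 (range 0.5 to 0.7).

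**1. The plan's own figure.** A two-sided t-test needs 44.59 per arm, rounded up to 45, with power 80.4% at 45. The stated sample size reproduces, and this point does not affect it.

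**2. Allocations known with certainty.** A block of 4 has 6 possible orders. The first two places match in 2 of the 6, so the chance that a place is already determined is 0, 0, 1/3 and 1 at positions 1 to 4.
- Mean: (1/3 + 1)/4 = 1/3.
- N = 90 is 22 complete blocks plus 2 students: 22 × 4/3 = 29.3, and 29.3/90 = 32.6%.

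**3. Best guess.** Always guess the arm with more places left, and toss a coin at ties. The success rates are 1/2, 2/3, 2/3 and 1.
- Mean: (17/6)/4 = 17/24 = 70.8%, against 50% with no information.
- At N = 90: (22 × 17/6 + 1/2 + 2/3)/90 = 63.5/90 = 70.6%.

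**4. Spurious difference with no true effect.** Suppose the student enrolled is δ better when video is guessed and δ worse when flashcards are guessed. With a fraction g of guesses correct, the arms differ by D = 2δ(2g − 1) = 2δ × 0.411 = 0.822δ.
- For δ = 0.1, 0.2 and 0.3, D = 0.08, 0.16 and 0.25 SD. Simulation gives 0.080, 0.162 and 0.244.

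**5. Unadjusted t-test.** SE = √(2/45) = 0.211, so D/SE = 0.39, 0.78 and 1.17. The normal approximation gives rejection rates of about 7%, 12% and 22%. Simulation gives 6.3%, 11.9% and 20.0%.

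**6. Planned ANCOVA.** SE = 0.211 × √(1 − 0.36) = 0.169.
- *Steered trait fully reflected in the pre-test:* the remaining bias is D(1 − ρ) = 0.4D = 0.03, 0.07 and 0.10 SD. Simulated error is about 6% to 8%. Runs across ρ = 0.5 to 0.7 give 5% to 9%.
- *Trait not reflected in the pre-test at all:* D is unchanged while the SE shrinks, so D/SE = 0.49, 0.97 and 1.46. The approximation gives about 8%, 16% and 31%, and a simulation run to check it gives about 8%, 15% and 28%. This exceeds the t-test's error, because ANCOVA estimates the same bias more precisely.

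**7. What the remedies change.**

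| Scheme | Certain predictions | Best guess right | D for δ = 0.1 to 0.3 | t-test type I error |
|---|---|---|---|---|
| Fixed 4 | 32.6% | about 71% | 0.08 to 0.24 SD | 6% to 20% |
| Random 4, 6, 8, order unknown | 2.3% | about 68% | 0.07 to 0.21 SD | 6% to 16% |
| One-step allocation after enrolment | cannot affect entry | cannot affect entry | 0 | 5% |

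The D and error columns for the first two rows are simulated.

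**The case against.** Fixed blocks of 4 in opaque envelopes are a common design, and the predictability figures are ceilings. They need students to be allocated one after another, by someone who knows the block size, sees earlier assignments in order and controls who enters next. The protocol says only that participants know their own arm. One course with electronic consent (Section 11) makes entry as a batch quite plausible, and then prediction could not affect who joins. The steering shift is assumed, and in the model it acts on every student, including those at tie positions where the guess is a coin toss. The 20% figure takes the largest assumed shift and ignores the planned ANCOVA. Varying the block size does little to best-guess success, so the fixed size is not the main driver; the order of enrolment and allocation is.

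Most of this stands, and it limits the claim. It does not remove it: the protocol's silence on entry order, custody and time of opening is why a reader cannot exclude the problem, and the envelopes do not settle it.

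A reader might infer more than the text supports:
- *That the block size was public during enrolment.* Section 13 makes documents available only after completion. The document is dated October 2025, while Section 4 places the study "during the Spring 2025 semester". Study staff could still have known the size.
- *That all earlier assignments were visible to enrolling staff.* Participants knowing their own arm does not establish this.

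**Conclusion.** The point holds conditionally. The arithmetic is exact: with blocks of 4 at 1:1, up to one third of allocations (about 29 of 90) can be known in advance and a simple guess is right about 71% of the time. Whether anyone could use this depends on sequential entry and on what enrolling staff knew, and the protocol is silent on both.

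The consequence rests on assumptions. For steering of 0.1 to 0.3 SD, type I error is about 6% to 20% with the unadjusted t-test. With ANCOVA it is about 6% to 8% if the pre-test captures the trait at ρ of about 0.6, and higher otherwise. None of this shows that selection occurred or that the trial's error rate is 20%. It is a weakness that should be closed because closing it costs almost nothing. It is not a reason to discount the design.

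**What to change.** **Preferred change to Section 6.** Complete consent and the pre-test for all students, then allocate the whole list in one step. This removes selection at entry whatever the block size, and should be feasible where all students share one course.

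**If entry must be sequential.** Use randomly varied block sizes (such as 4, 6 and 8), withhold them from enrolling staff, state who holds the list and envelopes, and open each envelope only after that student's pre-test is submitted. Certain predictions fall to a few percent, but best-guess success only from about 71% to 68%, so this is clearly second best.

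**If enrolment has already taken place.** Report the order of consent, pre-test and allocation, and who held the list and envelopes. Make the baseline-adjusted ANCOVA the main between-group comparison, noting that it protects only against differences that the pre-test measures.

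**Cost.** A sentence or two in Section 6 and, for varied blocks, a regenerated list; no extra students. Varied blocks may end slightly unequal: a 46/44 split has power 80.35% against 80.37% for 45/45. The present scheme can also end 46/44, since 90 is not a multiple of 4.

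### No outcome is named primary and no rule covers four outcomes and two unranked between-arm tests, so the false-positive rate across outcomes is not held at 5%

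*Combined protocol and SAP*

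**What the plan says.** - **Outcomes (Section 8).** There are four: knowledge (an "11-item multiple-choice questionnaire" scored 0–11), attitude, practice and confidence. None is labelled primary or secondary.
- **Analyses (Section 10).** Three kinds of test are listed without ranking: "Paired t-tests to assess within-group pre- and post-test changes", "Independent t-tests to compare between-group differences" and "ANCOVA to adjust post-test outcomes for baseline values". One rule covers all of them: "Significance threshold set at $p < 0.05". No testing order, adjustment or definition of overall success is given.
- **Sample size (Section 5).** With d = 0.6, alpha 0.05 and power 0.80, 45 per group "is required to detect statistically significant differences in post-test scores". Neither the outcome nor the test is named.
- **Objectives (Section 2).** Objective 1 is "To assess the impact of video-based education on EVD-related knowledge, attitude, practice, and confidence among nursing students". Objective 2 is the comparison of the two arms.
- **Expectation (Section 12).** Video is expected to be superior on knowledge, practice and confidence, with similar change in attitude. The section does not say whether one, some or all three must reach significance.
- **Context.** Students know their arm (Section 6). The flashcard session is described as "covering identical content without audiovisual elements" (Section 7). The title page is dated October 2025, and Section 4 places the study in Spring 2025.

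**The concern.** Each single test holds its 5%, but nothing limits the chance of a false positive across outcomes or across the two between-arm analyses. As written, a conclusion that video teaches better could rest on any one of four results, from whichever analysis gave the smaller p-value. Three of the four outcomes are self-ratings by students who know which material they received.

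The success rule is open in the other direction too. If all three outcomes in Section 12 must be significant, false positives are not inflated, but the stated 80% was worked out for one comparison and is not assured for three together. Sections 12 and 13 link the findings to curriculum change and education policy, so what counts as a positive trial should be settled in the plan.

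**Working it through.** **Inputs from the documents:** d = 0.6, alpha 0.05, power 0.80, 45 per group (Section 5); four outcomes (Section 8); threshold 0.05 per test, with an independent t-test and an ANCOVA (Section 10); three outcomes expected to be superior (Section 12).

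**Assumed, because the documents give no value:** a common between-outcome correlation r of 0, 0.5 or 0.8, and a pre-post correlation of 0.5 unless stated.

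**1. The plan's own figure.** Two-sided, two-sample t-test, noncentrality 0.6 × √(45/2) = 2.85 on 88 df: power is 80.4% at 45 per group and 79.5% at 44. So 45 is reproduced. A one-sided test would need only 36.

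**2. One two-sided 0.05 test per outcome, no true difference on any.** At r = 0 the chance of at least one false difference is 1 − 0.95^k, and of at least one favouring video 1 − 0.975^k, for k outcomes. For r > 0, equicorrelated normal statistics were integrated numerically: 1 − ∫ φ(u)[Φ((1.96 − √r·u)/√(1−r)) − Φ((−1.96 − √r·u)/√(1−r))]^k du. The lower limit is dropped for the one-directional figure.

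| | r = 0 | r = 0.5 | r = 0.8 | one test |
|---|---|---|---|---|
| Four outcomes, either direction | 18.5% | 15.6% | 11.4% | 5% |
| Four outcomes, favouring video | 9.6% | 7.8% | 5.7% | 2.5% |
| Three Section 12 outcomes, either direction | 14.3% | 12.5% | 9.8% | 5% |
| Three Section 12 outcomes, favouring video | 7.3% | 6.3% | 4.9% | 2.5% |

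For example, 1 − 0.95^4 = 0.185 and 1 − 0.975^3 = 0.073. Simulated t-tests with 45 per arm agree for four outcomes in either direction (18.5%, 15.6%, 11.5%).

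**3. Either the t-test or the ANCOVA may count.** In 60,000 simulated null trials of 45 per arm, at least one false difference over four outcomes occurred in about 26%, 22% and 16% at r = 0, 0.5 and 0.8. For a single outcome the figure is about 7%, so naming a primary outcome without naming its analysis would not restore 5%.

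**4. All three Section 12 outcomes must be significant, d = 0.6 on each.** By t-test at r = 0, 0.804³ = 0.52. Simulation (40,000 trials) gives 52%, 61% and 69% at r = 0, 0.5 and 0.8. By ANCOVA the range over r is about 73–82% at pre-post correlation 0.5, 58–73% at 0.3 and 93–95% at 0.7.

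**5. Power under the fix, 45 per group, d = 0.6.** ANCOVA acts roughly like a t-test with d/√(1 − 0.5²) = 0.6/0.866 = 0.69.

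| Two-sided level | t-test | ANCOVA |
|---|---|---|
| 0.05 (primary) | 80% | 90% |
| 0.05/3 = 0.0167 (first Holm step, three secondaries) | 66% | 80% |
| 0.05/4 = 0.0125 (first Holm step, all four) | 62% | 76% |

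**6. Holm over all four outcomes.** With one test per outcome and r = 0, the first step gives 1 − 0.9875^4 = 4.9%. If either test may count, simulation gives about 7%, between 6% and 7%, and 5% at r = 0, 0.5 and 0.8. One analysis therefore has to be fixed.

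**The case against.** **The larger figures overstate the risk of a false claim for video.** This stands in part. The 11–19% counts differences in either direction and includes attitude, on which Section 12 expects no advantage. For the three expected outcomes in video's favour, the figure is 5–7% against 2.5%. That is still two to three times the single-test rate, and the plan's threshold applies to all four outcomes in either direction.

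**The power calculation does have an analysis behind it.** This stands. A reader might infer that the sample size is wrong or is tied to no test. The documents do not support that: the 45 matches the two-sided independent t-test that Section 10 lists. What cannot be inferred is the outcome.

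**Paired tests might be used to claim superiority.** A reader might infer this from Objective 1 and the paired t-tests. The plan does not propose it. Section 10 ties those tests to within-group change and uses others to compare the arms, and Objective 2 is the between-arm comparison. One clarifying sentence is enough.

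**The dates might suggest that results had already been seen.** The October 2025 date follows the Spring 2025 semester, but nothing says that anyone had looked at results by arm. The order of events needs recording; it cannot be presumed.

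**Choosing knowledge as primary is a judgement.** True, since the documents do not rank the outcomes. The reason for the choice is that a multiple-choice test is the only one of the four that is not a self-rating.

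**Conclusion.** The concern holds and should be fixed. The stated threshold, applied as written, leaves error across outcomes uncontrolled:

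- about 11–19% for at least one false difference over four outcomes, or 6–10% favouring video;
- about 10–14% over the three outcomes in Section 12, or 5–7% favouring video;
- about 16–26% over four outcomes if either between-arm test may count.

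These figures assume no true difference on any outcome and between-outcome correlations of 0.8 to 0. The last also assumes a pre-post correlation of 0.5. The correlations are assumptions, but the excess over 5% remains even at 0.8.

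The sample-size arithmetic is sound for one two-sided t-test on one outcome. It does not assure 80% power for significance on all three expected outcomes: by t-test that is about 52–69%, and by ANCOVA it depends on the pre-post correlation.

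**What to change.** In Sections 5, 8 and 10:

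1. Name the one-week knowledge score (0–11) as primary, compared between arms by baseline-adjusted ANCOVA at two-sided 0.05. The independent t-test is supportive only.
2. Attach the power statement to knowledge. Say that the 80% is the unadjusted t-test figure and is conservative for ANCOVA.
3. Make practice, confidence and attitude secondary and label them self-reported. Test them by the same ANCOVA, with Holm at familywise 0.05, only if knowledge is significant. Otherwise report estimates with 95% confidence intervals.
4. State in one sentence that the within-group paired t-tests are descriptive and do not support a between-arm claim. Limit the Section 12 conclusion to match.
5. Record whether this choice preceded any view of results by arm. If it did not, label it post hoc and apply Holm across all four outcomes using the ANCOVA only.

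**Cost.** Wording only; N stays 90. First-step power for a secondary outcome falls to about 66% by t-test, or about 80% by ANCOVA at an assumed pre-post correlation of 0.5. Under the post hoc rule the first step has about 62% and 76%. None of this removes bias from unblinded self-rating.

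### Does predicting comparable attitude changes require an equivalence test or a margin in the plan?

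*Combined protocol and SAP*

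**What the plan says.** Section 12 (Expected Outcomes) forecasts "significantly greater improvements in knowledge, practice, and confidence compared to the flashcard group" and then adds "with comparable attitudinal changes". So three outcomes are expected to favour video and the fourth is expected to be similar in both arms.

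Section 10 treats all four outcomes alike. Between the arms it plans "Independent t-tests to compare between-group differences" and "ANCOVA to adjust post-test outcomes for baseline values", together with Cohen's d and 95% confidence intervals, at a 0.05 threshold. It contains no equivalence or non-inferiority hypothesis, no margin, and no rule for calling two arms comparable.

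Section 5 sets 45 per group (90 in total) for d = 0.6, alpha 0.05 and power 0.80, and says that this number "is required to detect statistically significant differences in post-test scores". It names no outcome.

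Section 2 lists three objectives: to assess the effect of the video, to compare improvements between the arms, and to explore correlations with baseline characteristics. None of them is to show equivalence.

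**The concern.** A prediction of similarity placed beside a plan made only of difference tests suggests a familiar error. If p < 0.05 is the only criterion, the apparent way to confirm the attitude prediction is to fail to reach it. A non-significant difference test does not show similarity at any sample size, and a small trial makes non-significance easy to obtain. A real attitude difference in either direction could then be published as comparable, and one of the four forecasts would be borne out by lack of power. Attitude is a listed outcome, and Section 13 intends the findings to feed nursing education policy, so a mistaken claim could be repeated.

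**Working it through.** **Inputs.** 45 per arm, d = 0.6, alpha 0.05 and power 0.80 come from Section 5; the analyses come from Section 10. The documents give no SD for the attitude scale, no correlation between baseline and post-test, and no margin. Results are therefore in SD units, and the correlations r and margins m below are assumptions shown over a range. No dropout is assumed.

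**1. The plan's own figure.** By normal approximation, n = 2 × ((1.960 + 0.842)/0.6)² = 43.6, so 44 per arm. The exact two-sided t calculation gives 44.59, so 45, with power 80.4%. The stated 45 reproduces as a two-sided superiority sample size.

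**2. Precision.** Unadjusted, SE = √(2/45) = 0.2108 SD, and the 95% half-width is t(0.975, 88) × SE = 1.987 × 0.2108 = 0.42 SD. A result just short of significance has an interval from about 0 to 0.84 SD. With ANCOVA, SE = √(2(1 − r²)/45). At r = 0.5 this is 0.1826, and the half-width is 1.988 × 0.1826 = 0.36 SD.

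**3. Chance of p ≥ 0.05 when the arms truly differ by d.** This is the probability that a noncentral t variable with noncentrality d/SE falls between −t(0.975) and +t(0.975), on 88 df unadjusted and 87 with ANCOVA.

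| True difference (SD) | Unadjusted | ANCOVA, r = 0.3 | ANCOVA, r = 0.5 |
|---|---|---|---|
| 0.3 | 71% | 69% | 63% |
| 0.4 | 53% | 50% | 42% |
| 0.5 | 35% | 31% | 23% |
| 0.6 | 20% | 16% | 10% |

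Missing a real difference is the more likely result at 0.3 SD, close to even at 0.4 SD, and the less likely result from 0.5 SD upward.

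**4. Power of a formal equivalence test.** For two one-sided tests at 5% with a true difference of 0, power ≈ 2Φ(m/SE − t(0.95)) − 1. For example, unadjusted at m = 0.4: 0.4/0.2108 − 1.662 = 0.235, giving 19%. Allowing for sampling variation in the SD changes the results by less than one percentage point; the table includes it.

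| Assumed margin (SD) | Unadjusted | ANCOVA, r = 0.3 | ANCOVA, r = 0.5 |
|---|---|---|---|
| 0.4 | 19% | 26% | 40% |
| 0.5 | 52% | 59% | 72% |
| 0.6 | 76% | 81% | 89% |

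Whether 90 participants are enough for an equivalence claim thus depends on a margin and a correlation that the documents do not give.

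**5. The texts side by side.** Section 12 states what is expected to happen. Section 2 does not ask for equivalence. Section 10 does not say how a non-significant result will be described, and it does commit to effect sizes and intervals. Following Section 10 to the letter gives an adjusted attitude difference with its 95% interval. No step in it produces a statement of comparability.

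**The case for a change.** The strongest case for a change is that a prediction stated in advance should come with a way to be confirmed or refuted. The three superiority predictions have one, in p < 0.05; the attitude prediction has none. The 95% intervals are the right raw material but give no verdict without a margin. ANCOVA helps without settling the matter, since at r = 0.5 a true difference of 0.3 SD is still missed 63% of the time. And the remedy looks cheap, a few words in Sections 10 and 12.

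Much of this stands. There is no margin, and p > 0.05 must not be written up as comparability. What does not follow is that the plan must change. An informal expectation of little difference on one of four outcomes does not turn the trial into an equivalence trial. The argument also supplies a step that the plan does not contain, namely reading non-significance as similarity.

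The possible remedies gain little. Reporting the adjusted difference with its interval repeats what Section 10 already implies. Calling attitude secondary would bring in a ranking of outcomes that Section 8 does not have. A margin would need an SD or an important difference on the attitude scale, and neither is given. The document is dated October 2025 for a study placed in Spring 2025, so a margin added now might not predate the data. A flat statement that 90 participants are too few would be wrong for some margins: at 0.6 SD, power is 76% unadjusted and 89% with r = 0.5.

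**Conclusion.** No change to the plan. The missing equivalence rule is a gap that a competent analyst fills when reporting: give the baseline-adjusted attitude difference with its 95% interval, and describe p > 0.05 as no difference demonstrated. The planned analyses already yield those numbers, and no stated rule leads to a wrong result.

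The uncertainty is real. The 95% half-width is about 0.42 SD unadjusted, or 0.36 SD with ANCOVA at r = 0.5, so a non-significant attitude result could not exclude a moderate difference. The published interval will show this to any reader. These figures assume 45 analysed per arm and equal SDs; the adjusted ones rest on assumed correlations. The conclusion would differ if the plan said that non-significance would be taken as comparability, or if showing comparability were an objective. Neither is so.
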